7.2 Analysis Populations

- **Per-Protocol Population:** The primary analysis includes all participants who completed the full course of 4 therapy sessions and underwent both baseline and final assessments.
- **Safety Population:** Safety analysis includes all participants who received at least one session of therapy.

7.3 Handling of Missing Data

Missing data points resulting from missed sessions or incomplete assessments were documented but excluded from the final efficacy calculation for that specific endpoint. No data imputation methods (e.g., Last Observation Carried Forward) were used. Analysis is based on observed cases only.

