4.0 Eligibility Criteria

4.1 Inclusion Criteria

- Confirmed clinical diagnosis of Parkinson's Disease.
- Hoehn and Yahr Scale Stage 3 or below (indicating mild to moderate disability).
- Ability to walk independently for approximately 5 minutes (with or without walking poles; Zimmer frames excluded).
- Age 18 to 75 years.

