6.0 Outcome Measures

6.1 Functional Mobility (Primary Outcome)

- **Metric:** 3-Meter Timed Up and Go (TUG) Test.
- **Method:** Participants were timed (in seconds) as they rose from a chair, walked 3 meters, turned around, walked back, and sat down.
- **Timing:** Assessed at Baseline (Session 1 Pre-Therapy) and Post-Intervention (Session 4 Post-Therapy).

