6.2 Functional Strength (Secondary Outcome)

- **Metric:** 30-Second Sit-to-Stand (STS) Test.
- **Method:** The number of full stands completed in 30 seconds was recorded.
- **Timing:** Assessed at Baseline and Post-Intervention.

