7.0 Statistical Considerations

7.1 Sample Size

As a pilot observational case series, the sample size (N=16) was determined based on feasibility and the capacity of the single-center clinical facility. The objective was to generate effect size estimates and standard deviation data sufficient to power a future randomized controlled trial (RCT). No formal power calculation was performed prior to recruitment.

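### A participant who attempts the final TUG and physically cannot finish it has no score under the plan and drops out of the primary analysis

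*Combined protocol and SAP*

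**What the plan says.** Section 7.3 (Handling of Missing Data) sets the rule: "Missing data points resulting from missed sessions or incomplete assessments were documented but excluded from the final efficacy calculation for that specific endpoint". The same section rules out imputation and bases the analysis on observed cases.

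Section 6.1 defines the primary outcome: "Participants were timed (in seconds) as they rose from a chair, walked 3 meters, turned around, walked back, and sat down". It sets no maximum time and no score for a test that is started and not finished.

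Section 7.2 limits the primary analysis to "all participants who completed the full course of 4 therapy sessions and underwent both baseline and final assessments".

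For sit-to-stand (STS), Section 6.2 says: "The number of full stands completed in 30 seconds was recorded".

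Section 7.4.2 compares baseline with final values by paired t-test, or by Wilcoxon signed-rank test for non-normal data, at the 0.05 level. Section 7.1 says the study is meant to supply effect sizes and standard deviations for powering a later randomised trial.

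No section distinguishes a test that was not done from one that was attempted and could not be completed.

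**The concern.** Failing to complete a mobility test for a physical reason is itself a mobility result, and the worst one possible. Because TUG is recorded only as a time to completion, that result has no number. The only rule in the plan that could apply to it is exclusion.

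A participant in this position may have had all four sessions and attended both assessments, so changing the analysis population in Section 7.2 would not bring them back. Section 6.1 places the final test after therapy at Session 4, and Section 5.0 gives a session as about 40 minutes, so stopping because of discomfort just after a session is conceivable.

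Two things are at stake. The reported mean TUG change could look favourable while someone had become unable to do the test. The effect size carried into the planning of the later trial would also come from finishers alone, with nothing in the report to say so.

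**Working it through.** **Inputs from the documents.** N = 16 (Section 7.1); paired t-test or Wilcoxon signed-rank test, threshold 0.05 (Section 7.4.2). Section 7.1 adds: "No formal power calculation was performed prior to recruitment". So the plan has no figure to reproduce.

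**Assumptions.** Two-sided testing (the plan does not state sidedness); one participant unable at final, leaving 15 finishers, unless stated otherwise; the finishers' changes as described below. The documents do not give the number unable, the size of the improvement or its SD.

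**Step 1: how the text handles the case.** TUG attempted and not finished → no time in seconds (6.1) → no cap or failure score to substitute (6.1) → nothing imputed, incomplete assessments excluded for that endpoint (7.3) → absent from the TUG comparison (7.4.2).

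**Step 2: Wilcoxon signed-rank test.** Place the 15 finishers' changes at the normal quantiles Φ⁻¹((i − 0.5)/15), i = 1 to 15 (SD 0.99), and shift them by d towards improvement. Let W be the sum of ranks of those who worsened. If the unable participant is dropped, n = 15 and the ranks total 15 × 16/2 = 120. If ranked as the worst change, that person takes rank 16, so W becomes W + 16, with n = 16 and a total of 136. The exact two-sided p is twice the lower tail at W.

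| d | W, dropped | p, dropped | W, ranked worst | p, ranked worst |
|---|---|---|---|---|
| 0.6 | 24 | 0.041 | 40 | 0.159 |
| 0.7 | 20 | 0.022 | 36 | 0.105 |
| 1.0 | 10 | 0.0026 | 26 | 0.029 |
| 1.2 | 5 | 0.0006 | 21 | 0.013 |

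With quantiles at i/16 instead, d = 0.6 gives 0.026 dropped and 0.117 ranked worst.

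In the most favourable case every finisher improves:
- one unable: 2/2¹⁵ = 0.00006 dropped; W = 16 gives 0.0052 ranked worst
- two unable: 2/2¹⁴ = 0.00012 dropped; W = 15 + 16 = 31 gives 0.058 ranked worst

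**Step 3: paired t-test.** Give the finishers mean improvement d and SD 1, so t = d√15 on 14 degrees of freedom. To include the unable participant, assign a worsening of m SD. Then mean = (15d − m)/16, SS = 14 + 15(d − mean)² + (m + mean)², SD = √(SS/15) and t = 4 × mean/SD on 15 degrees of freedom.

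Worked case, d = 0.8 and m = 2: mean = (12 − 2)/16 = 0.625; SS = 14 + 15 × 0.175² + 2.625² = 21.35; SD = 1.193; standardised change = 0.625/1.193 = 0.52; p = 0.054.

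For m from 2 to 4:
- d = 0.6: p goes from 0.036 to between 0.15 and 0.42
- d = 0.8: p goes from 0.008 to between 0.054 and 0.21
- d = 1.0: p goes from 0.0017 to between 0.018 and 0.10

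**Step 4: effect size.** At d = 0.8 the standardised change falls from 0.80 to 0.52 (m = 2) or 0.32 (m = 4). Required sample size scales as 1/d², so the ratio is (0.80/0.524)² ≈ 2.3 to (0.80/0.3245)² ≈ 6.1. This treats a within-group change as if it were the later trial's effect and depends on the assumed m, so it shows sensitivity only.

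**The case against.** The strongest reply is that Section 7.3 never mentions inability. Incomplete assessments could mean a test not administered or a form left blank, and such cases were documented. That is fair as to wording: the handling of inability is inferred. The inference stands because no other provision in the plan gives an unfinished TUG a value.

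The event should also be rare. Section 4.1 requires independent walking for about 5 minutes, the course lasts two weeks, and no case is reported. This limits the likely size of the bias but does not remove the gap.

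Serious events may appear in the adverse-event table (Section 7.4.3), which covers everyone given at least one session. That helps on safety but leaves the TUG estimate unchanged.

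A worst-rank test yields neither a mean nor an SD, which are what Section 7.1 wants. This stands, and it is why the worst-rank analysis belongs beside the finishers' mean rather than in its place.

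Four stronger readings are not supported:
- **STS has the same defect.** A reader might infer this, but a count of full stands makes zero an observed score. The plan merely omits to say so.
- **The rule can only flatter the result.** It would equally drop someone unable at baseline and able at final, the best possible change. The direction is clear only for inability arising after a timed baseline.
- **Stage 3 participants are most exposed.** Section 1.0 links postural instability to axial symptoms of the disease in general and names no stage.
- **One such case would overturn significance.** It can at d = 0.6 or 0.7. At d = 1.0 or 1.2 the Wilcoxon result survives.

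**Conclusion.** The point holds for TUG. Applied as written, Sections 6.1 and 7.3 together remove a participant who attempts the final test and cannot finish. For anyone with a timed baseline, that loss of function lowers N without worsening the mean change or the effect size.

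The actual size is unknown, and nothing in the documents shows that anyone was lost this way. Under the assumptions above, one such participant among 16 (1/16, about 6%) decides significance when the finishers' standardised improvement is about 0.6. It does not change the Wilcoxon conclusion at 1.0. The matter should be corrected before the TUG result is relied on for planning, but it does not show that the reported result is wrong. STS needs only a clarification.

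**What to change.** In Section 7.3, separate two categories: not assessed (missed visit, equipment or scheduling failure), which stays excluded, and attempted but physically unable. Take the reasons from the missing-data records that Section 7.3 says were kept, and report any unrecoverable reason as unknown.

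For TUG:
- report the number unable at baseline and at final beside the mean change
- state that the mean change applies to finishers only
- add a sensitivity analysis with the Wilcoxon signed-rank test already named in Section 7.4.2, ranking unable-at-final as the worst change and unable-at-baseline but able-at-final as the best

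For STS, add one sentence: an attempted test with no full stand is an observed score of 0.

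The cost is one paragraph in the analysis plan, a check of existing records and one extra test. The result may be somewhat less favourable. If the records show that nobody was unable, one sentence saying so closes the point.

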7.4 Statistical Methods

7.4.1 Descriptive Statistics

Baseline demographic and clinical characteristics (Age, Gender, Disease Duration) are summarized using means and standard deviations (SD) for continuous variables, and counts/percentages for categorical variables.

7.4.2 Efficacy Analysis

- **Primary Endpoint (Mobility):** The difference between Baseline (Pre-Intervention) and Final (Post-Intervention) TUG times was analyzed.
- **Secondary Endpoints:** Differences in STS counts, VAS Pain scores, and Sleep Quality scores were analyzed comparing Baseline to Final values.
- **Hypothesis Testing:** Paired t-tests were employed to assess the statistical significance of changes from baseline. For non-normally distributed data, the Wilcoxon signed-rank test was used.

- **Significance Level:** A p-value of <0.05 was considered statistically significant.
- **Calculations:** Percentage improvement was calculated as $((\text{Final Score} - \text{Baseline Score}) / \text{Baseline Score}) * 100$.

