6.3 Pain Intensity (Secondary Outcome)

- **Metric:** Visual Analog Scale (VAS).

- **Scale:** 0 (No Pain) to 10 (Worst Possible Pain).
- **Timing:** Assessed longitudinally throughout the study.

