6.4 Sleep Quality (Secondary Outcome)

- **Metric:** Self-Reported Likert Scale.
- **Scale:** 0 (Excellent) to 5 (Very Poor).
- **Timing:** Assessed longitudinally throughout the study.

STATISTICAL ANALYSIS PLAN (SAP)

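### Pain and sleep are scored repeatedly but compared only baseline to final, so scores from participants who stop early go unused and the completer difference can be biased

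*Combined protocol and SAP*

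**What the plan says.** Sections 6.3 and 6.4 give pain (0 to 10) and sleep (0 to 5) the same timing: "Assessed longitudinally throughout the study". Sections 6.1 and 6.2 restrict TUG and STS to two time points, so the repeated scoring of pain and sleep looks deliberate.

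Section 7.4.2 then treats all three secondary endpoints alike: "Differences in STS counts, VAS Pain scores, and Sleep Quality scores were analyzed comparing Baseline to Final values". The test is a paired t-test, or Wilcoxon signed-rank if the data are not normal. No model, summary measure or description of the time course uses the scores in between.

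Section 7.2 names one efficacy population, which requires all four sessions and both the baseline and final assessments. People with at least one session are kept for safety only. Section 7.3 removes missing points from the endpoint concerned, rules out imputation, and adds: "Analysis is based on observed cases only".

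**The concern.** Someone who stops after Session 2 or 3 may have two or three pain and sleep scores on record, and none of them reaches the efficacy result. If people whose pain is getting worse are more likely to stop, those who remain look better than the whole group, and a baseline-to-final difference in completers shows improvement that is not there.

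This matters because section 7.1 says the study is meant to supply effect sizes and SDs for powering a later randomised trial. An inflated change in pain or sleep would carry over into that calculation. With 16 participants, a few departures are enough to move the mean.

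**Working it through.** **1. Sections side by side.** The loss does not come from 7.4.2 alone. 7.4.2 requires a final score, 7.2 admits only completers, and 7.3 allows no substitute for a missing final score. 7.2 attaches its population to the primary analysis and names none for secondary endpoints. Even on the reading that it does not bind pain and sleep, 7.3 and 7.4.2 still exclude anyone without a final score.

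**2. Inputs.** From the documents: N = 16 ("the sample size (N=16) was determined based on feasibility and the capacity of the single-center clinical facility"), four sessions in two weeks, and "A p-value of <0.05 was considered statistically significant". Sidedness is not stated. I assume two-sided, so the nominal rate of false improvement is 2.5%. There is no planned figure to reproduce: "No formal power calculation was performed prior to recruitment". The documents give no SD, dropout rate, or number or timing of scores. Everything below on those is assumed.

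**3. Precision.** Let the correlation between any two scores be ρ. The variance of the completer difference is 2σ²(1 − ρ)/n. I compared it with the final-minus-baseline contrast from a model with a separate mean at each of four occasions and known covariance (ρ 0.5 to 0.9, compound symmetry or AR(1), early stoppers having two or three scores).

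| Stopping early, of 16 | Model variance / completer variance |
|---|---|
| 0 | 1.00 |
| 2 | 0.92 to 0.97 |
| 4 | 0.84 to 0.93 |

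For example, with ρ = 0.5 under compound symmetry, four stopping and two scores each, the completer variance is 2 × 0.5/12 = 0.083σ². The ratio of 0.917 brings it to 0.076σ². The gain is modest, and it is nil when nobody stops.

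**4. Bias.** Assumed model: score = person effect (SD 2) + person slope × session (SD 0.5 per session) + error (SD 1), four scores, no true mean change. Stopping after Sessions 2 and 3 has log-odds α + β × (current score − baseline score). With 4,000 replicates:

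| α, β | Mean completers | Completer bias (VAS points) | False improvement |
|---|---|---|---|
| -2.6, 1.0 | 12.1 | -0.38 | 9.5% |
| -3.5, 1.0 | 13.8 | -0.22 | 5.7% |
| -2.6, 0.5 | 13.4 | -0.18 | 4.8% |
| stopping unrelated to pain | not reported | about 0 | 2.7% |

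Other runs of the first row gave -0.38 to -0.41 and 9.0% to 10%. The SD of change in this model is √(3² × 0.5² + 2 × 1²) = √4.25 = 2.06. A bias of -0.38 is therefore a spurious standardised change of 0.38/2.06 = 0.18, and -0.22 is one of 0.11.

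**5. Which model removes it.** First-row scenario, 250 replicates:

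| Analysis | Bias | False improvement |
|---|---|---|
| Completer paired test | -0.41 | 10% |
| Random intercept only | -0.19 | 10% |
| Random intercept and slope, REML | -0.05 | 2.8% |

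The Monte Carlo error of a bias here is about 0.54/√250 = 0.03, and of a 10% rate about √(0.1 × 0.9/250) = 1.9 percentage points. The random-intercept model reports a standard error of 0.44 against an actual SD of 0.54. That is why it halves the bias without lowering the false-improvement rate. A run of 1,500 replicates, with a coarser fit of the same model, agreed: bias -0.14, false improvement 8.1%, standard error 0.46 against 0.55. Generalised least squares with the true covariance had bias 0.02, but that covariance is never known in practice.

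**The case against.** The case against acting is substantial. Baseline-to-final change is a legitimate target, these are secondary endpoints in a feasibility-sized single-arm series, and the course is short. If nobody stopped, there is neither bias nor gain: with a separate mean at each occasion the model's contrast equals the paired difference. All of that stands, and it limits how much weight the point can bear. It does not explain why scores collected repeatedly have no planned use.

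Four stronger readings are tempting and are not supported.

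- A reader might infer that any repeated-measures model cures the bias. It does not: under slope variation between people, a random intercept alone leaves about as much false improvement as the completer test. Without slope variation the random intercept suffices (bias 0.01, 2.7%), but the completer bias is then also smaller (-0.17, 5.8%).
- A reader might expect a 10% saving in variance. That figure comes from a straight-line trend over four equally spaced scores, where total change has variance 9σ²/5 = 1.8σ² against 2.0σ². It does not apply when each assessment has its own mean.
- A reader might take the unused scores as showing why people stopped. They may do so, but the documents do not say, nor how many stopped.
- A reader might choose pre-session scores at Sessions 1 and 4 as the contrast. That leaves out the effect of the fourth session and departs from TUG, whose final value is taken after Session 4.

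**Conclusion.** The gap is real. Pain and sleep are collected over time, only two points are analysed, and 7.2, 7.3 and 7.4.2 together discard the scores of anyone without a final value. The completer difference is biased if stopping depends on earlier scores.

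How large this is in the trial cannot be known from the documents. Under the assumed SDs, with stopping driven by observed worsening, it is about -0.2 to -0.4 VAS points with 14 to 12 of 16 completing. False improvement is about 6% to 10% against 2.5%, and nearer 5% when stopping depends more weakly on pain. The bias is zero if nobody stops or if stopping is unrelated to pain. The proposed model relies on stopping being explained by recorded scores; it does not repair stopping driven by unrecorded ones. The change is worth making because it is cheap, not because a bias has been shown.

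**What to change.** Amend 7.2, 7.3 and 7.4.2 together:

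- In 6.3 and 6.4, give the assessment times for pain and sleep, and define the final value as the one after Session 4, in line with TUG.
- Analyse each outcome with a REML mixed model on all observed scores from everyone with at least one session and a baseline score. Use assessment as a categorical effect, a random intercept and slope (or an unstructured covariance), and Kenward-Roger degrees of freedom. Fall back to a random intercept only on non-convergence, and say so if used.
- Report final minus baseline with a 95% CI. Where pre- and post-session scores both exist, do not pool them without a term that distinguishes them.
- Keep the paired t-test or Wilcoxon test in completers as a check, and tabulate how many stopped, when and why.
- The SAP is written in the past tense. If results have already been analysed, label the model post hoc.

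The cost is SAP wording and a little programming; it uses only scores already recorded. The drawbacks are fragile model fitting at N=16 and the fact that a linear model is only approximate for a 0-to-5 sleep item.

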3.0 Study Design

This was a prospective, single-arm, observational case series conducted at a single clinical site (The Manual Therapy Clinic, Edinburgh, UK).

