5.0 Study Intervention

Participants received therapy using the **BackHug** robotic spinal mobilization system.

- **Mechanism:** The device features 26 robotic therapeutic heads ('fingers') that deliver targeted deep-tissue pressure to the paraspinal muscles and intervertebral joints.
- **Regimen:** Participants attended four (4) sessions administered over a two-week period.
- **Duration:** Each session lasted approximately 40 minutes.
- **Settings:** Treatment intensity was personalized to user tolerance via the device's control app.

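### Section 7.4.2 labels uncontrolled single-arm changes as efficacy, but the tests show only whether the mean change differs from zero

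*Combined protocol and SAP*

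**What the plan says.** Section 3.0 sets out the design: "This was a prospective, single-arm, observational case series conducted at a single clinical site". No sham, untreated or delayed group is described, and blinding is not mentioned. Section 5.0 adds: "Treatment intensity was personalized to user tolerance via the device's control app". Pain is a 0 to 10 VAS (Section 6.3). Sleep is a 0 to 5 score described as a "Self-Reported Likert Scale" (Section 6.4).

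Section 7.4.2 carries the word 'efficacy' in its heading. It compares baseline with final values for TUG, STS, VAS pain and sleep: "Paired t-tests were employed to assess the statistical significance of changes from baseline", with the Wilcoxon signed-rank test for non-normal data. The threshold follows: "A p-value of <0.05 was considered statistically significant". It then defines a percentage 'improvement'. Section 7.3 also calls the endpoint results an efficacy calculation.

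Elsewhere the wording pulls in two directions. Section 1.0 states a causal hypothesis, that reducing axial stiffness improves mobility and lowers symptom burden. Section 2.0 speaks only of whether the intervention correlates with changes. Section 7.1 calls the study a pilot meant to supply effect sizes and SDs for powering an RCT.

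**The concern.** A paired test against zero bears on efficacy only if the change expected without any device effect is zero. With one arm and no comparator, nothing in the plan supports that. Participants presumably knew they were being treated. That is an inference from the single-arm design and the tolerance-based settings, but no other reading is plausible. Self-rated pain and sleep can shift with expectation. TUG and STS depend on effort and can shift with practice and motivation. Any of the four can move through regression to the mean or natural fluctuation.

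Two things are at stake. The first is what may be concluded: a significant result under this heading invites a reading as device efficacy that the design cannot support. The second is RCT planning: the observed mean change includes any non-device change, whereas a controlled trial estimates a difference in which a shared non-device change cancels.

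**Working it through.** **The plan's own figures.** Section 7.1 says "the sample size (N=16) was determined based on feasibility and the capacity of the single-center clinical facility" and "No formal power calculation was performed prior to recruitment", so there is no sample-size derivation to reproduce. The nominal level does reproduce: with zero true change, the two-sided paired t-test at n=16 rejects in 5.0% of studies.

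**Inputs.** From the documents: n=16 (7.1), threshold 0.05 and a test against zero change (7.4.2). Assumed: a two-sided test, since sidedness is not stated; no device effect; and a non-device mean shift of *d* SDs of the change score. The documents give neither a shift nor an SD of change, so *d* is shown as a range.

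**Formula.** With df = 15, the critical value is 2.131 and the noncentrality is λ = d√16 = 4d. The rejection probability is P(|T| > 2.131), where T is noncentral t with 15 df and noncentrality λ.

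| d | λ | P(p<0.05), n=16 |
|---|---|---|
| 0 | 0 | 5.0% |
| 0.1 | 0.4 | 6.6% |
| 0.2 | 0.8 | 11.6% |
| 0.3 | 1.2 | 20.3% |
| 0.5 | 2.0 | 46.5% |

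**Sensitivity.**
- Fewer completers (Sections 7.2 and 7.3 allow n below 16; the dropout rate is not stated). At d = 0.5: 41.0% for n=14, 35.3% for n=12, 29.3% for n=10. At d = 0.3: 18.0%, 15.8%, 13.6%.
- Wilcoxon at n=16, by simulation: about 19% at d = 0.3 and 43% at d = 0.5. Changing the test does not remove the problem.
- On the VAS, an assumed 1-point non-device drop gives 70.3%, 46.5%, 32.2% or 23.9% if the SD of change is 1.5, 2, 2.5 or 3.

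**RCT planning.** Suppose, as an assumption, that half of the observed mean change is non-device and would cancel between arms. Required sample size varies as 1/(effect)², so the true requirement is (1/0.5)² = 4 times the size planned on the full change. A trial planned for 80% power at two-sided 5% would then have power Φ(0.5 × (1.96 + 0.84) − 1.96) = Φ(−0.56), about 29%.

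**What n=16 does support.** A 95% CI for mean change has half-width 2.131/√16 = 0.53 SD of change. That interval is a usable description of change from baseline, but it is centred on the same uncontrolled mean and so does not remove the bias.

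**The case against.** A reader might infer that an expectation response will be reported as a significant device benefit far more often than 5% of the time. The documents do not support that. No section says a significant pain or sleep change will be called a device benefit. The test is correct at 5% for the statement it tests. The objectives use the language of correlation, and the study calls itself an observational pilot. The excess over 5% rests wholly on an assumed shift: it is trivial at 0.1 SD, about twofold at 0.2 SD, and fourfold only from about 0.3 SD. Section 4.1 sets no minimum pain or sleep problem at entry, so participants near the best score have little room to improve, which could keep the average shift small. All of this stands, and it makes the defect one of labelling and interpretation, not an invalid test.

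It does not clear the label. Section 7.4.2 plans no correlation with anything that varies between participants; it plans pre-post tests. The softer wording of the objectives does not reach the section that governs the analysis, where 'efficacy' and 'improvement' sit beside the causal hypothesis of Section 1.0. The pilot purpose does not help either, because effect sizes are exactly what the study is meant to pass on.

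A reader might also infer faults in how ratings were collected, such as anchoring on earlier answers or a wish to please the therapist. The documents describe no assessor or rating-form procedure, so neither can be asserted.

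**Conclusion.** The point holds as a mismatch between label and design. The planned tests support the statement that mean change differs from zero, and no more. The mismatch covers all four endpoints and is greatest for self-rated pain and sleep. Its numerical size cannot be fixed from the documents. Over assumed non-device shifts of 0.1 to 0.5 SD of change with no device effect, the chance of p<0.05 per endpoint runs from 6.6% to 46.5% at n=16, and is lower with fewer completers. These figures illustrate what a significant result could mean; they do not estimate this study's error rate. For a self-described pilot the consequence is limited to the wording of conclusions and the use of its mean changes in planning the RCT.

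**What to change.** 1. Rename Section 7.4.2 as change from baseline, and replace the efficacy wording in Section 7.3 to match.
2. Report TUG, STS, VAS pain and sleep each as mean change with SD and 95% CI.
3. State that p<0.05 on any endpoint means change from baseline only and will not be described as efficacy or device benefit, in line with the objectives in Section 2.0.
4. State that the uncontrolled mean changes include non-device change. A future RCT should take the SDs from this study but should not use the mean change, unadjusted, as its target between-group effect. This sentence is needed because a CI alone carries the same bias forward.

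The documents are written in the past tense, so data collection appears to be over; no change to assessments is proposed, and none is needed for these steps. The cost is SAP and report wording. The downside is a less favourable headline.

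### The percentage-of-baseline formula in SAP section 7.4.2 does not exclude the sleep rating, which has no real zero, so a sleep percentage would have no interpretable size

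*Combined protocol and SAP*

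**What the plan says.** Protocol section 6.4 measures sleep on a "Self-Reported Likert Scale" scored "0 (Excellent) to 5 (Very Poor", so lower is better. SAP section 7.4.2 brings sleep into the efficacy analysis: "Differences in STS counts, VAS Pain scores, and Sleep Quality scores were analyzed comparing Baseline to Final values". For inference, it states that "Paired t-tests were employed to assess the statistical significance of changes from baseline", with the Wilcoxon signed-rank test for non-normal data.

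The last item of the same section gives the percentage formula, introduced by "Percentage improvement was calculated as". It is written for a generic score, and no endpoint is excluded. The section does not say whether the percentage is taken per participant and then averaged, or from the group means. It gives no rule for a baseline of 0.

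**The concern.** A change divided by its baseline means something when zero stands for none of the quantity measured. TUG seconds and STS counts meet that condition, and 0 on the pain VAS is no pain. On the sleep item, 0 is the name of the best category. The numbers order the answers but do not measure a distance from a natural origin, so dividing by one of them gives a figure that depends on where the numbering starts and which way it runs.

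At stake is the description of one secondary outcome. Improvement in sleep is a stated secondary objective (section 2.0), and the study has one arm and 16 participants. A reader who sees a sleep percentage beside the TUG and STS percentages will take them as comparable, and they are not. Eligibility (sections 4.1 and 4.2) sets no minimum level of sleep problem, so participants with baselines of 0 or 1, where the formula fails or is most extreme, can enter.

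**Working it through.** The documents contain no sleep result and no percentage, so there is no figure to reproduce. The check applies the plan's formula to assumed ratings. Whole-number ratings are also assumed; section 6.4 labels only the two ends.

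**Inputs.** The scale is 0 (best) to 5 (worst), from section 6.4. The formula is % = (Final - Baseline)/Baseline x 100, from section 7.4.2. N = 16, from section 7.1. The individual scores are illustrative.

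**1. One participant, one category better, coded as in section 6.4**
- 5 to 4: (4 - 5)/5 = -20%
- 4 to 3: (3 - 4)/4 = -25%
- 3 to 2: (2 - 3)/3 = -33.3%
- 2 to 1: (1 - 2)/2 = -50%
- 1 to 0: (0 - 1)/1 = -100%
- Any change from 0: division by zero

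The same one-step improvement varies five-fold (100/20).

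**2. Percentage from group means, 3.0 at Baseline and 2.5 at Final**
- Coded 0 to 5 as written: (2.5 - 3.0)/3.0 = -16.7%
- Coded 1 to 6: (3.5 - 4.0)/4.0 = -12.5%
- Reverse-scored 0 to 5: (2.5 - 2.0)/2.0 = +25%

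All three describe better sleep, and the size varies two-fold (25/12.5).

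**3. Sixteen participants: 10 move from 4 to 3 (better), 6 move from 1 to 2 (worse)**

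As coded, the Baseline mean is (40 + 6)/16 = 2.875 and the Final mean is (30 + 12)/16 = 2.625. The mean change is -0.25 category, an improvement.
- Percentage from group means: -0.25/2.875 = -8.7%, an improvement.
- Mean of individual percentages: (10 x (-25) + 6 x 100)/16 = 350/16 = +21.9%, a worsening.

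The same answers under four numberings:

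| Numbering | Mean change | From group means | Mean of individual % |
|---|---|---|---|
| 0 to 5, as written | -0.25 | -8.7% (better) | +21.9% (worse) |
| 1 to 6 | -0.25 | -6.5% (better) | +6.3% (worse) |
| Reversed, 0 to 5 | +0.25 | +11.8% (better) | +53.1% (better) |
| Reversed, 1 to 6 | +0.25 | +8.0% (better) | +23.8% (better) |

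On these data the paired t-test gives p = 0.333 and the Wilcoxon test p = 0.317 in every row.

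**4. How often the contradiction arises.** The group in step 3 was chosen to show that it can happen. In 20,000 simulated groups of 16, baselines were uniform on 1 to 4 and changes of -2, -1, 0 and +1 had probabilities 0.15, 0.35, 0.30 and 0.20, with Final scores kept within 0 to 5. The mean individual percentage showed worsening while the mean change showed improvement in 2.6% of groups. That rate belongs to this assumed distribution only.

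**5. What depends only on order.** In step 3, the counts are 10 improved, 0 unchanged and 6 worsened under any numbering that keeps the order. The raw mean change is not as robust. With unequal scores 0, 3, 6, 7, 8, 9 for the six categories it becomes (6 x 3 + 10 x (-1))/16 = +0.5, a worsening. This is why the counts are worth showing beside it.

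**The case against.** The best defence has four parts.

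- **The coding is fixed.** Section 6.4 states the numbers and their direction. The other numberings are hypothetical, and no choice of coding is left to the analyst. This stands. The alternative codings show that the percentage has no natural unit. They do not show that the plan is ambiguous about scoring.
- **Direction is mostly safe.** A reader might infer that the direction of the sleep result depends on the coding, or that good sleepers always weigh more than poor ones. The documents do not support either as a general statement. Both need individual percentages to be averaged, and section 7.4.2 does not say that they were. From group means, every participant's change counts equally. Shifting the codes then alters only the size, and reversing them flips the arithmetic sign without changing whether sleep got better or worse.
- **The objective does not rest on the percentage.** Section 7.4.2 analyses the raw differences and tests the changes. The percentage is a separate calculation with no test attached. Section 7.1 seeks effect sizes and standard deviations for a later trial and does not mention percentages. A reader might infer that the planned test is invalid, or that sleep should have the Wilcoxon test alone. Neither follows: both p-values are the same when the codes are shifted or reversed.
- **The formula does not name sleep.** This is true, but it is unrestricted and follows a list of endpoints that includes sleep. If sleep was never meant to be covered, one sentence saying so settles the matter.

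These points narrow the concern to the reported percentage. They do not rescue it, because its size depends on the numbering under either way of computing it.

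**Conclusion.** The concern holds as a minor reporting correction to one secondary outcome. As written, the plan produces a sleep percentage whose size cannot be interpreted: a five-fold spread for the same one-category step in individuals, and a two-fold spread across numberings in the illustrative group means. For an individual, it is undefined at a baseline of 0.

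A contradiction with the direction of the raw change (+21.9%, a worsening, against a mean improvement of 0.25 category) is possible only if individual percentages are averaged, and it is not the usual outcome. No primary result, analysis population or p-value is affected.

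This rests on three assumptions: the unrestricted formula covers sleep, ratings are whole numbers, and the illustrative scores show what the formula does, not what the trial found.

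**What to change.** In SAP section 7.4.2, state that Sleep Quality is excluded from the percentage calculation. For sleep, report the raw Baseline-to-Final change, with a Baseline-by-Final shift table giving the numbers improved by at least one category, unchanged, and worsened by at least one category. Leave the planned hypothesis test as stated.

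The cost is a sentence in the SAP, one small table and the loss of a percentage that could not be interpreted. No new data are needed. The plan is written in the past tense, so the analysis may already be complete. If it is, label the added table as a reporting change made after the analysis.
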